7.3.4.2 Follow up visit at 1-month (Visit 5, Day 30 +/- 10)

- Obtain medical history
- Record adverse events as reported by participant or observed by investigator (if applicable)
- Targeted physical exam
- Administration of study questionnaires
- Previous / concomitant treatments, including medical history
- Peripheral venous blood draw and urine sample to perform follow-up laboratory tests

CONFIDENTIAL

- Note: Subjects will be required to withhold pain medications 24 hours prior to screening and each visit for the evaluation of pain

7.3.4.3 Follow up visit at 3 months (Visit 6, Day 90 +/- 10)

- Obtain medical history
- Record adverse events as reported by participant or observed by investigator (if applicable)
- Targeted physical exam
- Administration of study questionnaires
- Previous / concomitant treatments, including medical history
- Peripheral venous blood draw and urine sample to perform follow-up laboratory tests
- Follow-up knee MRI
- Note: Subjects will be required to withhold pain medications 24 hours prior to screening and each visit for the evaluation of pain

7.3.4.4 Follow up visit at 12 months (Visit 7, Day 360 +/- 10)

- Obtain medical history
- Record adverse events as reported by participant or observed by investigator (if applicable)
- Targeted physical exam
- Administration of study questionnaires
- Previous / concomitant treatments, including medical history
- Peripheral venous blood draw and urine sample to perform follow-up laboratory tests
- Note: Subjects will be required to withhold pain medications 24 hours prior to screening and each visit for the evaluation of pain

7.3.5 Follow up visit at 18-48 month (visit 8):

- This visit is optional to all study participants who completed 12 months visit by August 31, 2024 and fall within 18-48 months window from the date of procedure. This visit is not expected to add significant risk to participant and will only occur after obtaining informed consent from participants. This visit is important to add at this point of the trial to obtain long term follow up data.
- Obtain medical history
- Record adverse events as reported by participant or observed by investigator (if applicable)
- Targeted physical exam
- Administration of study questionnaires
- Previous / concomitant treatments, including medical history
- Peripheral venous blood draw and urine sample to perform follow-up laboratory tests
- Note: Subjects will be required to withhold pain medications 24 hours prior to screening and each visit for the evaluation of pain

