
1- If not previously available (i.e., recent knee MRI within 3 months of screening); if MRI cannot be obtained on the same day due to subject preference and/or MRI scheduling related reasons, MRI can be performed anytime between the baseline visit and intervention visit
 
2- If not previously available (i.e., recent knee radiograph within 6 months of screening). Can be performed on a separate day based on appointment availability or subject's preference.
 
3- Post-procedural MRI can be done on a separate day of visit 6 based on appointment availability and subject's preference as long as it's performed within the timeframe of 3month +/- 10 days.
 
* Visit 1 and 2 can be combined based on subject preference. In that case, procedures listed in visit 2 will be performed after signing informed consent on the same day.
 
** Visit 4 (1-day follow-up) dates range can be +3 days (phone call, telemedicine, or in-person IR clinic visit determined by subject's preference and need for physical examination)
 
*** Visit 8. Optional visit for participants who completed 12 month follow up by August 31, 2024 (by invitation, voluntary, and after obtaining informed consent for this visit). This visit can be performed at any time interval within 18 months – 48 months
								

CONFIDENTIAL

post procedure. This visit can be performed by sending the questionnaire by a safe email and participants can email it back to research coordinator or PI OR by a phone call performed by research coordinator,
	
# 1, 3, 12-month follow-up dates range can be +/- 10 days
	
## The pre-procedural blood work can be done on the day of the procedure prior to performing the procedure based on subject's preference.
	
--	--	--	--

1 Key Roles

- **Principal Investigator (PI):** Will be one of two interventional radiologists performing the procedure. Will be responsible for study integrity, data monitoring, data collection, statistical analysis, and manuscript writing.

[name]

Clinical Assistant Professor of Radiology
Director, Vascular and Interventional Radiology Research Program
Department of Radiology, NYU Langone Health
[name]
[contact]
Email: [contact]

- **Co-PI:** Co-investigator involved in recruiting patients and conducting the clinical assessment for knee osteoarthritis

[name]

Associate Professor
Department of Internal Medicine, NYU Langone Orthopedic Center
[name]

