4.2.2 Secondary Study Endpoints Analysis

Secondary efficacy endpoints are:

- 1- WOMAC pain score at 1- and 12- months (and final 18-48 months visit) post intervention
- 2- Pain electronic VAS at 1-, 3-, and 12- months (and final 18-48 months visit) post intervention
- 3- Knee stiffness WOMAC score at 1-,3-, and 12- months (and final 18-48 months visit) post intervention
- 4- Physical function WOMAC score at 1-, 3-, and 12- months (and final 18-48 months visit) post intervention
- 5- Total WOMAC score at 1-,3-, and 12- months post intervention
- 6- Self-reported quality of life using EQ-5D-5L scale at 1-, 3-, and 12- months (and final 18-48 months visit) post intervention.
- 7- MRI findings at 3- months post intervention
- 8- Pain medication usage at 1-, 3-, and 12- months (and final 18-48 months visit) post intervention
- 9- Injection therapy requirements (hyaluronic acid or steroid) at 12- months (and final 18-48 months visit) post intervention
- 10- Physical therapy requirements at 12- months (and final 18-48 months visit) post intervention
- 11- Feasibility / technical success
- 12- Laboratory findings at 1-, 3-, and 6- months (and final 18-48 months visit) post intervention

Secondary safety endpoints are:

- 13- Number/rate, severity, and description of complications, adverse events, or poor outcomes that are secondary to the procedure, which will be summarized using counts and simple statistics (i.e., mean number of patients with complications.)

CONFIDENTIAL

5 Study Enrollment and Withdrawal

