5.7 Participant Withdrawal or Termination

5.7.1 Reasons for Withdrawal or Termination

Participants are free to withdraw from participation in the study at any time upon request. Participation of a patient in this clinical study may be discontinued for any of the following reasons:

- The patient withdraws consent or requests discontinuation from the study for any reason;
- Occurrence of any medical condition or circumstance that exposes the patient to substantial risk and/or does not allow the patient to adhere to the requirements of the protocol;
- Any AE, clinically significant adverse event, severe laboratory abnormality, intercurrent illness, or other medical condition that indicates to the investigator that continued participation is not in the best interest of the patient;
- Pregnancy during study period;

CONFIDENTIAL

- Patient failure to comply with protocol requirements or study-related procedures;
- Termination of the study by the Sponsor, the regulatory authority, FDA, or IRB.
- The participant meets an exclusion criterion (either newly developed or not previously recognized) that precludes further study participation
- Progression of osteoarthritis requiring surgical therapy
- Patients found to have osteonecrosis on pre-procedural MRI

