5.7.2 Handling of Participant Withdrawals or Termination

If a patient withdraws prematurely from the study due to the above criteria or any other reason, study staff should make every effort to complete the full panel of assessments scheduled for the follow-up visits. The reason for patient withdrawal must be documented in the electronic case report form (eCRF). In the case of loss of follow-up, attempts to contact the patient will be made and documented in the patient's medical records. Every effort will be made to undertake protocol-specified safety follow-up procedures to capture AEs, serious adverse events (SAEs), and unanticipated problems (UPs).

Withdrawn patients can be replaced.

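### Only 12-month completers can enter the 18-48 month visit, so the long-term secondary endpoints leave out most patients who left early and probably overstate lasting benefit

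*Combined protocol and SAP*

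**What the plan says.** **Entry to Visit 8.** Section 7.3.5 states: "This visit is optional to all study participants who completed 12 months visit by August 31, 2024". It also requires that the patient be 18 to 48 months from the procedure. The Protocol Summary (Participant Duration), the Schedule of Activities footnote and Section 7.2.1 repeat the completion condition. The footnote adds a second filter: the visit is "by invitation, voluntary, and after obtaining informed consent for this visit".

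**Use of the data.** Section 4.2.2 lists among the secondary efficacy endpoints "WOMAC pain score at 1- and 12- months (and final 18-48 months visit) post intervention". It also names the final visit for pain VAS, WOMAC stiffness and function, EQ-5D-5L, pain medication, injections and physical therapy. Section 10.4.3 promises an estimate and 95% confidence interval for each secondary outcome at each time, with paired tests against baseline for the scores.

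**Leaving the study.** Section 5.7.1 allows discontinuation for "Progression of osteoarthritis requiring surgical therapy", for "Any AE, clinically significant adverse event, severe laboratory abnormality, intercurrent illness, or other medical condition" that makes staying unwise in the investigator's view, and where "The patient withdraws consent or requests discontinuation from the study for any reason". Lack of effect is not named. After withdrawal, Section 5.7.2 says that "study staff should make every effort to complete the full panel of assessments scheduled for the follow-up visits"; it also allows withdrawn patients to be replaced.

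**Analysis set.** Section 10.3 keeps only participants who attend all follow-up visits. Section 10.1 says there will be no formal SAP. No section gives a missing-data method, a rule for counting target-knee surgery in the long-term outcomes, or a statement that Visit 8 results describe completers only.

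**The concern.** Section 7.3.5 presents Visit 8 as the source of long-term follow-up data. Whether a patient can contribute depends on something that happens after treatment, namely staying to month 12. The protocol itself links leaving to outcome, because progression to surgery and adverse events are both listed grounds for discontinuation. A patient who has knee surgery at month 8 and leaves is an informative long-term case, but would normally supply no Visit 8 data. Target-knee surgery is also not an endpoint in Section 4.2.2, so the loss would not show up elsewhere in the results.

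Without a control arm there is no comparator against which to judge the selection. What is at stake is the meaning of the 18-48 month scores. They would describe patients who stayed a year and then volunteered, and could be read as describing everyone treated.

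**Working it through.** **1. The plan's own figure.** Section 5.6 requires 40 patients with data and accrues 50 for 20% attrition: 40 / (1 - 0.20) = 50. This reproduces. It is an accrual allowance for the primary objective (Section 5.4), not an estimate of loss between embolization and month 12. The 20% is borrowed below only to give a scale.

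**2. Route into Visit 8 under the text as written.**

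| Patient | Eligible for Visit 8? |
|---|---|
| Attends month 12 by the cut-off, responder | Yes, if in the window and willing |
| Attends month 12 by the cut-off, non-responder | Yes, on the same terms |
| Leaves before month 12 (surgery, adverse event, own request) | No, unless the month-12 assessments are still obtained under Section 5.7.2 |
| Stays in the study but misses month 12 | No |

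The filter is attendance at month 12, followed by acceptance of the invitation. The 31 August 2024 date is administrative and not in itself related to outcome.

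**3. Effect of the completion filter (illustration).** Let d be the share of treated patients who do not reach month 12, c the long-term response rate in completers and m the rate in non-completers.

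Rate in all treated = (1 - d) × c + d × m

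Assume d = 0.20, c = 0.75 and that every completer is seen:

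| m (assumed) | All treated | Excess of completer rate |
|---|---|---|
| 0 | 0.80 × 0.75 + 0 = 60% | 15 points |
| 0.25 | 0.60 + 0.05 = 65% | 10 points |
| 0.50 | 0.60 + 0.10 = 70% | 5 points |
| 0.75 | 0.60 + 0.15 = 75% | 0 |

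**4. Adding voluntary uptake (illustration).** Assume 50 treated, 40 eligible and an observed response of 75%. The lower bound counts every unseen patient as a non-responder, the upper bound as a responder.

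| Seen | Responders | Unseen of 50 | Range for all treated |
|---|---|---|---|
| 40 | 30 | 10 | 30/50 = 60% to 40/50 = 80% |
| 24 | 18 | 26 | 18/50 = 36% to 44/50 = 88% |
| 20 | 15 | 30 | 15/50 = 30% to 45/50 = 90% |

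These bounds lie on both sides of 75%. The arithmetic therefore shows how little the observed patients pin down. The expectation of overstatement comes from the withdrawal reasons in Section 5.7.1, not from the arithmetic.

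**5. Limits of the illustration.** The plan defines a responder only at 3 months (Sections 3.1, 10.2 and 10.4.2). At 18-48 months it would report scores and treatment use. The response rate is used here because it makes the selection easy to see; the same selection acts on mean scores.

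**The case against.** The strongest reply has five parts.

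- **Failure is not a bar.** A reader might infer that everyone in whom treatment failed is shut out. The documents do not support that: lack of effect is not a listed reason for withdrawal, and a non-responder who attends month 12 can be invited. This stands.
- **Withdrawn patients are not always lost.** Discontinuation is permitted rather than required for the listed reasons. Section 5.7.2 asks staff to complete the scheduled assessments, and Section 7.3.6 provides an early-termination visit. A withdrawn patient whose month-12 assessments were completed might qualify. This stands as an exception. It creates no Visit 8 route for those without month 12, and Section 10.3 still works against them.
- **The number excluded is unknown.** A reader might infer that 10 of 50 treated patients are barred. Accrued is not the same as embolized: attrition can precede the procedure (for example, osteonecrosis on the pre-procedural MRI), and withdrawn patients can be replaced. The number meeting the date and window conditions is not given either. This stands, so the figures above are illustrations only.
- **Some of the data are already collected.** Visit 8 includes medical history, adverse events and treatments, and injection use is already an endpoint there. True, but only for people allowed to attend, and no rule says how surgery counts.
- **This is an optional extension of a single-arm pilot.** It drives no decision rule and no durability hypothesis is stated. That limits the seriousness of the point but does not remove it, because these data are named secondary endpoints with promised estimates and tests.

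**Conclusion.** The concern holds as a selection problem in the long-term secondary endpoints. Patients who leave before month 12 generally cannot enter Visit 8, and Section 10.3 reinforces their absence. Since progression to surgery and adverse events are among the reasons for leaving, long-term benefit is likely to be overstated.

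The documents do not determine by how much. If 20% of treated patients miss month 12 and all completers are seen, a 75% completer response overstates the all-treated rate by 0 to 15 points as the non-completer response falls from 75% to none. A reader might take the 15 points as the bias. It is the extreme case, in which no non-completer responds. Incomplete uptake widens the uncertainty in both directions.

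The Visit 8 entry condition has no bearing on the 3-month primary endpoint. This is a change that should be made, not one on which the trial's main conclusion depends.

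**What to change.** 1. **Invitation.** In Section 7.3.5, the Protocol Summary, the Schedule footnote and Section 7.2.1, extend the Visit 8 invitation to every embolized patient within 18 to 48 months of the procedure who has not withdrawn consent for contact, whether or not month 12 was completed. Use the existing phone or email option, for which Section 7.2.1 already waives samples.
2. **Data.** Add target-knee surgery and repeat embolization since Day 0, with dates, to the Visit 8 form.
3. **Analysis set.** Amend Section 10.3 so that these patients are included in the long-term analysis, and reconcile it with the post-withdrawal follow-up in Section 5.7.2. Without this, the wider invitation would collect data that the plan then discards.
4. **Reporting.** Show the numbers treated, eligible, invited and seen, with reasons for non-entry. Label any completer-only scores as conditional on 12-month completion and on uptake.
5. **Sensitivity analysis.** Repeat the long-term analysis with target-knee surgery counted as an unfavourable outcome.

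The cost is an amendment, consent wording and a small number of extra contacts, with no new procedure. If the sponsor declines the wider invitation, the labelling and participant counts still need only text, and surgery can be counted as unfavourable wherever it is known from the withdrawal record.

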7.3.6 Withdrawal/Early Termination Visit

- Obtain medical history
- Record adverse events as reported by participant or observed by investigator (if applicable)
- Targeted physical exam

CONFIDENTIAL

- Administration of study questionnaires
- Previous / concomitant treatments, including medical history
- Peripheral venous blood draw and urine sample to perform follow-up laboratory tests
- Note: Subjects will be required to withhold pain medications 24 hours prior to screening and each visit for the evaluation of pain

7.3.7 Unscheduled Visit

Unscheduled visits if needed will be documented in the medical chart of the subject including the reason for the visit and assessment / management plan as determined by the visit.

7.4 Concomitant Medications, Treatments, and Procedures

All relevant concomitant medications taken during study participation, as well as treatments and procedures will be recorded on eCRFs. Medications to be reported in the eCRF are concomitant prescription medications, over-the-counter medications and non-prescription medications used pain management. For this protocol, a prescription medication is defined as a medication that can be prescribed only by a properly authorized/licensed clinician.

Note: Subjects will be required to withhold pain medications 24 hours prior to screening and each visit for the evaluation of pain

7.5 Rescue Medications, Treatments, and Procedures

In the event of non-target embolization during the procedural visit leading to limb ischemia, subsequent interventions and / or medical management may be required for treatment of limb ischemia.

7.6 Participant Access to Study Agent at Study Closure

After participants are no longer enrolled in the study, they will return to standard of care treatment for knee OA.

8 Assessment of Safety

8.1 Specification of Safety Parameters

Safety parameters include the number, severity, causality, timing, and description of complications, adverse events, or poor outcomes that are secondary to the procedure.

CONFIDENTIAL

This material is the property of the NYU School of Medicine and Langone Medical Center. Do not disclose or use except as authorized in writing by the study sponsor
Interventional Template Version: 12 February 2020

8.1.1 Definition of Adverse Events (AE)

An **adverse event** (AE) is any symptom, sign, illness or experience that develops or worsens in severity during the course of the study. Intercurrent illnesses or injuries should be regarded as adverse events. Abnormal results of diagnostic procedures on target knee in the follow-up period after the study intervention are considered to be adverse events if the abnormality:

- results in study withdrawal
- is associated with a serious adverse event
- is associated with clinical signs or symptoms
- leads to additional treatment or to further diagnostic tests
- is considered by the investigator to be of clinical significance

8.1.2 Definition of Serious Adverse Events (SAE)

Serious adverse events are considered to be those resulting in an unplanned increase in the level of care, prolonged hospitalization, permanent adverse sequelae, or death.

A **serious adverse event** is any AE that is:

- fatal
- life- or limb- threatening
- requires or prolongs hospital stay
- results in persistent or significant disability or incapacity
- a congenital anomaly or birth defect
- an important medical event

Important medical events are those that may not be immediately life or limb threatening but are clearly of major clinical significance. They may jeopardize the subject and may require intervention to prevent one of the other serious outcomes noted above.

All adverse events that do not meet any of the criteria for serious should be regarded as **non-serious adverse events**.

8.1.3 Definition of Unanticipated Problems (UP)

Unanticipated Problems Involving Risk to Subjects or Others

Any incident, experience, or outcome that meets all of the following criteria:

- Unexpected in nature, severity, or frequency (i.e. not described in study-related documents such as the IRB-approved protocol or consent form, the investigators brochure, etc)
- Related or possibly related to participation in the research (i.e. possibly related means there is a reasonable possibility that the incident experience, or outcome may have been caused by the procedures involved in the research)
- Suggests that the research places subjects or others at greater risk of harm (including physical, psychological, economic, or social harm).

CONFIDENTIAL

Unanticipated adverse device effect, any serious adverse effect on health or safety or any life-threatening problem or death caused by, or associated with, a device, if that effect, problem, or death was not previously identified in nature, severity, or degree of incidence in the investigational plan or application, or any other unanticipated serious problem associated with a device that relates to the rights, safety, or welfare of subjects (21 CFR 812.3(s)).

8.2 *Classification of an Adverse Event*

8.2.1 **Severity of Event**

The Investigator will assess the severity (intensity) of each adverse event as mild, moderate, severe, life-threatening / disabling event, or death/ unexpected pregnancy abortion. The investigator will also categorize each adverse event as to its potential relationship to study drug using the categories of yes or no.

The severity and causality of all adverse events will be graded according to the new adverse event classification by the Society of Interventional Radiology Standards of Practice Committee [30], as follows:

- **Mild AE:** No therapy or nominal (non-substantial) therapy (postprocedural imaging performed and fails to show manifestation of AE); near miss (eg, wrong site of patient prepared, recognized and corrected before procedure, wrong patient information entered for procedure);
- **Moderate AE:** moderate escalation of care, requiring substantial treatment, eg, intervention (description of intervention and result of intervention) under conscious sedation, blood product administration, extremely prolonged outpatient observation, or overnight admission after outpatient procedure not typical for the procedure (excludes admission or hospital days unrelated to AE);
- **Severe AE:** marked escalation of care, ie, hospital admission or prolongation of existing hospital admission for > 24 hours, hospital admission that is atypical for the procedure, inpatient transfer from regular floor/telemetry to intensive care unit, or complex intervention performed requiring general anesthesia in previously non-intubated patient (generally excludes pediatrics or in circumstances in which general anesthesia would primarily be used in lieu of conscious sedation, eg, in mentally challenged or severely uncooperative patients);
- **Life-threatening or disabling event:** eg, cardiopulmonary arrest, shock, organ failure, unanticipated dialysis, paralysis, loss of limb or organ;
- **Patient death or unexpected pregnancy abortion.**

For AEs not included in the protocol defined grading system, the following guidelines will be used to describe severity.

- **Mild** – Events require minimal or no treatment and do not interfere with the participant's daily activities.
- **Moderate** – Events result in a low level of inconvenience or concern with the therapeutic measures. Moderate events may cause some interference with functioning.
- **Severe** – Events interrupt a participant's usual daily activity and may require systemic drug therapy or other treatment. Severe events are usually potentially life-threatening or incapacitating.

8.2.2 **Relationship to Study Device**

CONFIDENTIAL

For all collected AEs, the clinician who examines and evaluates the participant will determine the AE's causality based on temporal relationship and his/her clinical judgment. The degree of certainty about causality will be graded using the categories below according to the new adverse event classification by the Society of Interventional Radiology Standards of Practice Committee

- Category 1: AE not caused by procedure. The AE is completely independent of study drug administration, and/or evidence exists that the event is definitely related to another etiology. There must be an alternative, definitive etiology documented by the clinician.
- Category 2: Unknown whether AE was caused by the procedure.
- Category 3: AE caused by the procedure. There is clear evidence to suggest a causal relationship, and other possible contributing factors can be ruled out.

The definition implies a reasonable possibility of a causal relationship between the event and the study device. This means that there are facts (evidence) or arguments to suggest a causal relationship.

The following factors should also be considered:

- The temporal sequence from study procedure: The event should occur after the study procedure. The length of time from study procedure to event should be evaluated in the clinical context of the event.
- Underlying, concomitant, intercurrent diseases: Each report should be evaluated in the context of the natural history and course of the disease being treated and any other disease the patient may have.
- Concomitant procedures / treatments: The other drugs the patient is taking or the treatment the patient receives should be examined to determine whether any of them might be recognized to cause the event in question.
- Known response pattern for this class of study procedure: Clinical and/or nonclinical data may indicate whether a particular response is likely to be a class effect.
- Exposure to physical and/or mental stresses: The exposure to stress might induce adverse changes in the recipient and provide a logical and better explanation for the event.

